### **5.5 Efficacy Analysis**

#### **5.5.1 Primary Efficacy Analysis**

The FAS and the PPS will be used for the analysis of the primary efficacy analysis.

The primary endpoint is the proportion of patients who experience the first US within the first 6 months (until Day 182) after randomisation (failure rate). First US within the first 6 month, deaths before the first US and patients without evaluable assessment of the primary endpoint will be counted as treatment failures. The first occurring event will be used for this analysis e.g. if a patient experiences an US and dies later, this patient will be included as a patient with an US. If a patient experienced a re-stroke, the patient will be counted as a withdrawal with the date of re-stroke as ‘Date of withdrawal’.

To show that ESL is different to placebo, the primary null hypothesis

$$H_0: p_{ESL} \geq p_{placebo}$$

will be tested against the alternative hypothesis

$$H_1: p_{ESL} < p_{placebo}$$

where  $p_{ESL}$  and  $p_{placebo}$  denote the proportions of patients with the first US within 6 months after randomisation in ESL and placebo patients, respectively.

The primary hypotheses will be assessed in the FAS by means of a chi-square test with continuity correction on the significance level of 5% (two-sided, which corresponds to the significance level of

2.5% one-sided). The Odds Ratio for Placebo vs. ESL and the corresponding 95% score CI will be provided. The Risk Difference (RD) of failing between Placebo and ESL with corresponding 95% continuity-corrected Newcombe Confidence Interval (CI) for the risk difference Placebo – ESL will be calculated. Additionally, the p-value of Fisher's exact test will be provided.

For this purpose, the following SAS code will be used:

**Note: Data should be sorted by descending treatment group (first “ESL” then “Placebo”) and by treatment failures (first “Failure” then “Non-failure”).**

```
PROC FREQ DATA = <dataset> order=data;
  TABLE <Treatment group> * < Treatment Failure>
    /CHISQ RISKDIFF (CL =Newcombe (Corrected)) OR(CL =SCORE) ALPHA=0.05;
RUN;

PROC FREQ DATA = <dataset> order=data;
  tables <Treatment group> * < Treatment Failure>/ fisher;
run;
```

The following statistical outputs will be created:

Table 15.2.1.1.1 Analysis of Treatment Failure Rate within 6 Months after Randomisation – Full Analysis Set

Table 15.2.1.1.2 Analysis of Treatment Failure Rate within 6 Months after Randomisation – Per-Protocol Set

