### **5.5.1.1 Sensitivity Analyses**

For the primary analysis, patients withdrawing early during the trial will be considered as non-seizure free (treatment failure). This replacement strategy is defined under the assumption that it cannot be excluded that “missingness” is related to treatment failure and thus not at random. In order to assess the effect of missing data, the following sensitivity analyses will be performed:

The primary analysis will be repeated by imputing the missing values (patient withdrew from study before primary endpoint was reached) in both groups (ESL and Placebo) multiple times assuming the rate of treatment failures among the missing data follows the observed rate of treatment failures in the placebo group.

The following SAS code will be used:

**Note: Treatment Failure will be 1 if a patient had an US or died, 0 if not and ‘.’ if the data is missing (patient withdrew). A dummy baseline variable that consists only 0 will be created. Treatment group will be 1, if the patient received ESL and 2 if the patient received placebo. n will be the number of patients that experienced at least one US until 6 months.**

```
proc mi data=<data> seed=14823 nimpute=&n. out=<out> noint;
  class <Treatment group> <Treatment Failure>;
  var <Baseline Dummy> <Treatment Failure>;
  monotone logistic(<Treatment Failure> /detail);
  mnar model(<Treatment Failure> / modelobs=(trt='2'));
run;
```

The chi-square test as described in 5.5.1 will be applied to each of the imputed datasets. The results will be pooled by Rubin's rule. For the Odds Ratio, the logarithm will be applied before pooling and afterwards the exponential function will be applied:

```
DATA lgsodds_t;
  SET < DATA ODDS>;
  log_or_lr_value=LOG(ODDSRATIO);
  log_or_lr_se=(LOG(UPPERCL)-LOG(LOWERCL)) / (2*1.96);
RUN;
*** Combine transformed estimates;
PROC MIANALYZE DATA=lgsodds_t;
  ODS OUTPUT PARAMETERESTIMATES=mian_lgsodds_t;
  MODELEFFECTS log_or_lr_value;
  STDERR log_or_lr_se;
RUN;
*** Back-transform combined values;
DATA mian_lgsodds_bt; SET mian_lgsodds_t;
  Estimate_back = EXP(ESTIMATE); *Pooled odds ratio;
  LCL_back=Estimate_back*EXP(-1.96*STDERR); *Pooled lower limit;
  UCL_back=Estimate_back*EXP(+1.96*STDERR); *Pooled upper limit;
RUN;
```

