A tipping point analysis based on multiple imputation relating the outcome of the primary efficacy analysis to the assumed rate of treatment failure among missing data under ESL and placebo, respectively, will be performed. In the primary analysis, patients with missing data will be classified as 'treatment failure'. By contrast, the tipping point analysis proceeds as follows: Assuming there will be  $N = 1, \dots, n$  missing values for patients in the treatment group and  $M = 1, \dots, m$  missing values for the patients in the placebo group.  $N * M$  datasets will be created, one for each possible combination of imputation for the missing values ('treatment failure' or 'treatment success').

The chi-square test presented in the primary analysis 5.5.1 will be conducted for each of the datasets. Results will be tabulated and p-values will be presented via a heatmap where significant and non-significant p-values will be differently colored. .

Another sensitivity analysis will be conducted based on observed Unprovoked Seizures only as Failure Rate. Death, Withdrawals or patients with missing data will not be counted as a Failure but as a Non-Failure. The primary efficacy analysis will be repeated for this scenario.

The following statistical outputs will be presented:

[Table 15.2.1.3.1 Sensitivity Analysis of Treatment Failure Rate within 6 Months after Randomisation Using Multiple Imputation for Missing Data – Full Analysis Set](#)

[Table 15.2.1.3.2 Sensitivity Analysis of Treatment Failure Rate within 6 Months after Randomisation Using Multiple Imputation for Missing Data – Per-Protocol Set](#)

Degrees of freedom (DF), value and p-value for chi-square test, RD of failing between ESL and Placebo with corresponding 95% continuity-corrected Newcombe CI as well as ESL vs Placebo OR with 95% score confidence interval for the multiple imputed datasets that are combined by Rubin's Rule will be presented.

Table 15.2.1.4.1 Tipping Point Analysis of Treatment Failure Rate within 6 Months after Randomisation – Full Analysis Set

Table 15.2.1.4.2 Tipping Point Analysis of Treatment Failure Rate within 6 Months after Randomisation – Per-Protocol Set

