Degrees of freedom (DF), value and p-value for chi-square test, RD of failing between ESL and Placebo with corresponding 95% continuity-corrected Newcombe CI as well as ESL vs Placebo OR with 95% score confidence interval will be presented for all possible combinations of imputed non-failures in ESL and Placebo arm.

Table 15.2.1.5.1 Sensitivity Analysis of Unprovoked Seizures within 6 Months after Randomisation – Full Analysis Set

Table 15.2.1.5.2 Sensitivity Analysis of Unprovoked Seizures within 6 Months after Randomisation – Per-Protocol Set

Table 15.2.1.5.3 Sensitivity Analysis of Unprovoked Seizures within 12 Months after Randomisation – Full Analysis Set

Table 15.2.1.5.4 Sensitivity Analysis of Unprovoked Seizures within 12 Months after Randomisation – Per-Protocol Set

Table 15.2.1.5.5 Sensitivity Analysis of Unprovoked Seizures within 18 Months after Randomisation – Full Analysis Set

Table 15.2.1.5.6 Sensitivity Analysis of Unprovoked Seizures within 18 Months after Randomisation – Per-Protocol Set

Table 15.2.1.5.7 Sensitivity Analysis of Unprovoked Seizures within 18 Months after Randomisation (Subgroup 1) – Full Analysis Set

Table 15.2.1.5.8 Sensitivity Analysis of Unprovoked Seizures within 18 Months after Randomisation (Subgroup 2) – Full Analysis Set

Number and percentage of unprovoked seizures and non-failures 6, 12 or 18 months after randomisation will be tabulated, including degrees of freedom (DF), value and p-value for chi-square test, p-value for Fisher's exact test, RD of failing between ESL and Placebo with corresponding 95% continuity-corrected Newcombe CI as well as ESL vs Placebo OR with 95% score confidence interval.

Figure 15.2.1.1.1 Tipping Point Analysis of Treatment Failure Rate within 6 Months after Randomisation – Full Analysis Set

Figure 15.2.1.1.2 Tipping Point Analysis of Treatment Failure Rate within 6 Months after Randomisation – Per-Protocol Set

Results (p-values) of the tipping point analysis will be presented via heatmap.

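### SAP 5.5.1.1 ties the number of imputations to the seizure count, promises pooled results that Rubin's rule cannot supply, and contradicts itself on the size of the tipping-point grid (low impact: sensitivity analyses only)

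*SAP*

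**What the plan says.** SAP 5.5.1 defines the primary test, which is "assessed in the FAS by means of a chi-square test with continuity correction" with deaths and patients without an evaluable endpoint counted as failures. SAP 5.5.1.1 then sets out the missing-data checks.

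- **Multiple imputation.** "The primary analysis will be repeated by imputing the missing values" in both arms, at the failure rate observed on placebo. The code has `nimpute=&n.` and a fixed seed of 14823, and the note above it says that "n will be the number of patients that experienced at least one US until 6 months".
- **Pooling.** The 5.5.1 test is "applied to each of the imputed datasets. The results will be pooled by Rubin's rule". Code is given for one quantity only, the log odds ratio.
- **Output.** Tables 15.2.1.3.1 and 15.2.1.3.2 are to hold "Degrees of freedom (DF), value and p-value for chi-square test, RD of failing between ESL and Placebo", with a continuity-corrected Newcombe interval and an odds ratio with a score interval, "for the multiple imputed datasets that are combined by Rubin's Rule will be presented".
- **Tipping point.** With N = 1, …, n missing values on ESL and M = 1, …, m on placebo, N × M "datasets will be created, one for each possible combination of imputation for the missing values". Results "will be presented for all possible combinations of imputed non-failures in ESL and Placebo arm".

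**The concern.** These analyses exist to show whether the primary result survives other assumptions about withdrawn patients. A reader will set the pooled p-value beside the primary one, so it should not hang on the seed or on an unrecorded programming choice.

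The number of imputations controls Monte Carlo error and should follow from the missing data or be a large constant. A seizure count does neither. It falls as recruitment falls (SAP 2.6 says recruitment stopped short, without giving the number reached), and it leaves out failures that are deaths. A fixed seed makes the result repeatable, not precise.

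Rubin's rule combines an estimate with its variance. A chi-square value has no such variance, and a Newcombe interval is not built from a single standard error, so the tables as described cannot be filled from the rule named. The one quantity with code, the log odds ratio, carries no continuity correction, although the primary analysis is said to be repeated.

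**Working it through.** Write K for the number of imputations, to keep it apart from the n and m of the tipping-point text. All patient counts below are assumed, because the documents give no outcome data and no final sample size. K is set to its largest possible value, with every observed failure a US.

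**1. Planned case.** The protocol's sample size section assumes failure rates of 26% and 8% and 5% missing per arm. Its adjusted rates reproduce: 0.95 × 26% + 5% = 29.7%; 0.95 × 8% + 5% = 12.6%. Per 100 patients that is about 25 and 8 observed failures (24.7 and 7.6) and 5 missing per arm, so K is at most 33.

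**2. Small K.** The between-imputation variance is B = Σ(q_k − q̄)²/(K − 1). At K = 1 the divisor is zero; at K = 0 nothing is imputed. At full recruitment the expected K is at most 26 + 8 = 34, since those rates include deaths. If the overall seizure rate is 5% to 17% (assumed), the chance that K is 0 or 1 is 12% to 74% with 20 patients in total, 0.5% to 40% with 40, and near 0 to 9% with 80.

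**3. Primary test.** X² = N(|ad − bc| − N/2)² / (product of the four margins), missing counted as failure:

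| Case | Failures, ESL vs placebo | X² | p |
|---|---|---|---|
| Planned, 100 per arm | 13 vs 30 | 200 × 1600²/(43 × 157 × 100²) = 7.58 | 0.006 |
| A: 60 per arm, 5 and 10 missing, 5 vs 13 observed | 10 vs 23 | 120 × 720²/(33 × 87 × 60²) = 6.02 | 0.014 |
| B: as A, 5 vs 14 observed | 10 vs 24 | 120 × 780²/(34 × 86 × 60²) = 6.94 | 0.008 |

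**4. Multiple imputation as worded.** The placebo log-odds is drawn from its approximate posterior and missing outcomes in both arms are imputed from it. Two pooled tests are compared:

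- Log odds ratio by Rubin's rule, t reference.
- D2 on the corrected chi-square values d_k: r = (1 + 1/K) × var(√d_k); D = [mean(d_k) − r(K + 1)/(K − 1)]/(1 + r); F with 1 and (K − 1)(1 + 1/r)² degrees of freedom.

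Ranges cover the middle 95% of seeds (20,000 seeds for K = 18 and 19, otherwise 4,000); in brackets, the share of seeds below 0.05.

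| Case | K | D2 p | Log-OR p |
|---|---|---|---|
| Planned | 33 | 0.003–0.006 | 0.003–0.005 |
| A | 18 | 0.045–0.103 (7%) | 0.032–0.073 (56%) |
| A | 1000 | 0.063–0.070 (0%) | 0.045–0.050 (97%) |
| B | 19 | 0.028–0.067 (73%) | not needed here |
| B | 1000 | 0.040–0.045 (100%) | not needed here |

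A large K settles the seed question. It does not settle the rule. In case A at K = 1000 the median p is 0.067 by D2, 0.047 by log odds ratio, 0.045 from a plain mean of the chi-square values, and 0.038 from the risk difference by Rubin's rule (15.5 points, 95% CI 0.9 to 30.2).

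**5. Tipping grid.** An arm with n missing values can have 0 to n imputed failures, so every combination means (n+1)(m+1) datasets. With 5 missing per arm that is 36, against 5 × 5 = 25. With 5 missing in one arm and none in the other it is 6, against 0. For 100 per arm and 8 vs 24 observed failures, the cell worst for ESL is 13 vs 24: X² = 200 × 1000²/(37 × 163 × 100²) = 3.32, p = 0.069. It is the only non-significant cell in the full grid. The largest p in the 25-cell grid is 0.047 if N and M count failures, 0.043 if they count non-failures. Among placebo counts 18 to 30, only 24 shows this loss.

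**6. Code.** The results in step 4 follow the SAP's words. The code pairs `noint` with an all-zero dummy. If that means no intercept, the linear predictor is 0 and outcomes are imputed at 50%, against 13/50 = 26% observed on placebo in case A. Case A at K = 18 would then give D2 p 0.032–0.083 (42%). What SAS actually does here was not tested.

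**The case against.** Much of the opposing case stands.

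- **Risk difference.** A reader might infer that nothing in the SAP can pool it. That is too strong: Rubin's rule is named and works for a risk difference with a standard error. Only the source of the standard error is unstated, and only the Newcombe interval is out of reach.
- **Grid.** A reader might infer that the SAP defines a grid that hides the worst case for ESL. The documents do not establish that. The formula omits the zero rows, but the wording beside it and in the table description asks for all combinations. This is a contradiction, and the literal reading changes the heatmap's message at one placebo count in the range examined.
- **Seed.** Case A's 56% on the log odds ratio is tempting as a headline, but the tables list no p-value for the odds ratio. With D2 the same data give 7%, a mostly stable conclusion. The like-for-like illustration is case B.
- **Selected examples.** Cases A and B need a smaller trial, twice as much missing data on placebo, and a result close to 0.05. With equal missing data (15 of 100 per arm, 8 vs 20; or 9 of 60, 5 vs 14) the primary test is already non-significant (p = 0.087 and 0.114), so there is no significant result to undermine. Nor does the SAP require the imputation p-value to fall below 0.05.
- **Choice of remedy.** K = 1000 and D2 are each one adequate choice, and in case A the choice of D2 decides the side of 0.05. That is a reason to name a rule while blinded, whichever rule it is.

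None of this supplies a sound number of imputations or a way to fill the chi-square row.

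**Conclusion.** The point holds, at low impact. The imputation count is tied to the wrong quantity and has no floor; the pooled chi-square result and Newcombe interval cannot come from the rule named; and the two descriptions of the tipping grid disagree. The documents do not support reading this as a threat to the primary result: the primary test uses none of these rules, and the planned-rate example gives p below 0.01 under both rules. What is exposed is a sensitivity p-value near 0.05, where it can cross the line with the seed (case B, 73% of seeds below 0.05 at K = 19) or with the pooling rule (case A, 0.038 to 0.067 even at K = 1000). Those sizes rest on assumed counts, on every failure being a US, and on imputation at the observed placebo rate, which the code may or may not deliver.

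**What to change.** Before unblinding, amend SAP 5.5.1.1:

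1. Set `nimpute` to a fixed large constant, for example 1000, and keep the seed.
2. Name one rule for the pooled test that keeps the continuity correction, for example D2 on the corrected chi-square values, and fill the chi-square row of Tables 15.2.1.3.1 and 15.2.1.3.2 from it.
3. Pool the risk difference by Rubin's rule with a stated standard error, and show that interval in place of the Newcombe one.
4. State the tipping grid as 0 to n by 0 to m imputed failures, (n+1)(m+1) datasets.
5. Check that the `noint` and all-zero-dummy code imputes at the observed placebo rate. Otherwise 1000 imputations would only estimate an unintended model more precisely.

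The cost is a few lines of text, a short programming check and seconds of computing. No new data are needed.

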## **5.5.2 Analysis of Secondary Efficacy Variables**

The FAS and the PPS will be used for the analysis of secondary efficacy variables.

All data will be analysed as reported and missing data will not be imputed.

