### **2.2 Study Endpoints**

#### **2.2.1 Primary Efficacy Endpoints**

The primary endpoint of this trial is the proportion of patients who experience the first US within the first 6 months after randomisation. Deaths before the first US or patients without evaluable assessment of the primary endpoint (i.e. drop-outs independently of the reason) will be counted as treatment failures (failure rate).

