### **4.1 General Methodology and Presentation of the Results**

The default summary statistics for quantitative (continuous) variables will be

- the number of patients with data at the visit (n),
- number of patients with missing data (nmiss),
- mean,
- standard deviation (SD),
- median,
- first quartile (Q1) and third quartile (Q3)
- minimum (min) and maximum (max)

for patients with data.

Mean, median, and the quartiles will be presented to one more decimal place than the raw value. The minimum and maximum values will be presented with the same decimal precision as the raw value. SD will be reported to two decimal places greater than the original value.

For qualitative (categorical) variables, the number (n) and percentage (%) of patients with non-missing data per category will be the default frequency tabulations. Where appropriate and present, the number of missing values will be displayed as “Missing” category.

Percentage values are to be presented to one decimal place, for example, 52.3%.

The denominator used for calculation of the percentages will be specified in a footnote to the tables for clarification.

All reported p-values will be two-sided. No adjustment for multiplicity will be performed.

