## **Endpoint value**

The endpoint value for an efficacy variable is defined as the last non-missing value collected after first intake of IMP before or at the respective endpoint (within the time window of interest i.e. 6 month-period, 12 month-period and 18 month-period).

The endpoint for a safety variable is defined as the last non-missing value collected after first intake of IMP that is no baseline value.

**Absolute change from baseline** will be calculated as

$$\text{Absolute Change from Baseline at Visit } X = \text{Value at Visit } X - \text{Baseline Value}$$

**Relative change from baseline (%)** will be calculated as

$$\text{Relative Change from Baseline at Visit } X = \frac{\text{Value at Visit } X - \text{Baseline Value}}{\text{Baseline Value}} \times 100$$

Note: Patients with a baseline value of '0' will be excluded from the calculation of relative change.

See section 5.4.1 for the definition of first and last IMP intakes.

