## **4.10 Handling of Missing Data**

The analysis of missing data impact on the primary efficacy endpoint is described in the Section 5.5.1.1.

All other data will be analysed as reported and missing data will not be imputed.

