#### **5.5.2.5 Barthel Index**

BI data is collected at V1a, V3, V5, V7 and EOT or EDV and, if applicable, UNS.

The BI is a widely used score to measure the performance in activities of daily living of patients with stroke and other neuromuscular or musculoskeletal disorders in the following 10 categories:

1. Feeding (scored as 0, 5, 10)
2. Moving from a wheelchair to a bed and back again (scored as 0, 5, 10, 15)
3. Personal hygiene (scored as 0, 5)
4. Getting on and off the toilet (scored as 0, 5, 10)
5. Self-bathing (scored as 0, 5)
6. Walking on a level surface (scored as 0, 5, 10, 15)
7. Ascending and descending stairs (scored as 0, 5, 10)
8. Dressing (scored as 0, 5, 10)
9. Controlling bowels (scored as 0, 5, 10)
10. Controlling bladder (scored as 0, 5, 10)

Items are weighted according to the level of nursing care required and are rated in terms of whether individuals can perform activities independently, with some assistance, or are dependent (scored as 0, 5, 10 or 15). The total BI score (possible range 0 – 100) will be calculated as the sum of the individual scores from each item.

General ranges of BI describe patients' disability as follows:

80-100 – patient should be able to live independently

60-79 – minimally dependent

40-59 – partially dependent  
20-39 – very dependent  
<20 – total dependence.

The BI can be used to determine a baseline level of function and to monitor improvements in activities of daily living over time [4].

The BI total score at baseline and post-baseline visits of each patient will be calculated adding the individual scores from each item.

The BI total score and its change from baseline at each time of examination will be summarised by means of descriptive statistics. Differences between the treatment groups (ESL-Placebo) will be evaluated exploratively using multiple exact Wilcoxon-Mann-Whitney Test and exact Hodge-Lehmann CIs at each time of examination.

The following SAS Code will be used:

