**Note: Data should be sorted by treatment group (first “ESL” then “Placebo”)**

```
proc npar1way hl correct=no alpha=.05 data=<dataset>;
  class <treatment_group>;
  var <change from baseline of BI_total_score at specific timepoint>;
  exact wilcoxon;
  exact hl;
  ods select WilcoxonScores WilcoxonTest HodgesLehmann;
run;
```

If this SAS code runs for more than 10 minutes, maxtime=50 will be used and the normal approximate result will be tabulated. A higher maxtime does not lead to a change of the result.

Cumulative incidence of USs will be illustrated using Kaplan-Meier curves by the BI Baseline categories (<=79, 80-100) and treatment group. Patients without an event or lost to follow-up will be censored at their last visit or termination date. Time to event will be calculated from time of randomisation to first US.

The following statistical outputs will be presented:

[Table 15.2.6.1.1 Summary of Barthel Index Total Score – Full Analysis Set](#)

[Table 15.2.6.1.2 Summary of Barthel Index Total Score – Per-Protocol Set](#)

The default summary statistics for the BI total score will be presented by visit slots by treatment group at Baseline, V3, V5, V7, EOT, EDV (if applicable) and Endpoint.

[Table 15.2.6.2.1 Analysis of Barthel Index Total Score Differences – Full Analysis Set](#)

[Table 15.2.6.2.2 Analysis of Barthel Index Total Score Differences – Per-Protocol Set](#)

The Hodges-Lehmann estimate of location shift and the corresponding 95% CIs including the Wilcoxon Mann Whitney test p-value will be presented by visit slots for V3, V5, V7 and Endpoint for ESL-Placebo.

[Figure 15.2.2.1 Cumulative Incidence Curves of Unprovoked Seizures using Kaplan-Meier Curves by Barthel Index Total Score – Full Analysis Set](#)

[Figure 15.2.2.2 Cumulative Incidence Curves of Unprovoked Seizures using Kaplan-Meier Curves by Barthel Index Total Score – Per-Protocol Set](#)

Cumulative incidence curves of USs using Kaplan-Meier curves displayed by time of randomisation and treatment group for each category of the BI total score.

[Listing 16.2.3.3 Barthel Index – Enrolled Set](#)

The BI items and total score data will be listed by treatment group.

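### Barthel Index and NIHSS are tested between arms with no handling of death, so unequal, selective mortality would bias the visit tests towards the arm with more deaths and be largely hidden at Endpoint

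*SAP*

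**What the plan says.** - **Missing data.** SAP 5.5.2 states for the secondary efficacy variables: "All data will be analysed as reported and missing data will not be imputed". SAP 4.10 applies the same rule to everything except the primary endpoint: "All other data will be analysed as reported and missing data will not be imputed".
- **Test.** For BI, SAP 5.5.2.5 says: "Differences between the treatment groups (ESL-Placebo) will be evaluated exploratively using multiple exact Wilcoxon-Mann-Whitney Test". The SAS code there takes change from baseline in BI total score as the test variable. SAP 5.5.2.6 plans the same test for NIHSS but gives no code; I assume the same variable.
- **Time points.** For BI, "The Hodges-Lehmann estimate of location shift and the corresponding 95% CIs including the Wilcoxon Mann Whitney test p-value will be presented by visit slots", namely V3, V5, V7 and Endpoint, with the same list for NIHSS. EOT is summarised but is not in the difference tables (15.2.6.2.x and 15.2.7.2.x), so any 18-month comparison rests on Endpoint.
- **Endpoint.** SAP 4.8 has it "defined as the last non-missing value collected after first intake of IMP before or at the respective endpoint", with no exception for death.
- **Death elsewhere.** In the primary endpoint (SAP 2.2.1), "Deaths before the first US or patients without evaluable assessment of the primary endpoint" count as failures, and the 12- and 18-month failure rates follow suit. Death is a competing risk in SAP 5.5.2.3 and the event in the overall-survival analysis of SAP 5.5.2.8. None of these is joined to BI or NIHSS.

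**The concern.** A patient who has died has no change from baseline at a later visit. Take a patient with BI 60 at V3 who dies on Day 100 with no further score. This patient is absent at V5 and V7 and enters the 18-month Endpoint as 60 minus the baseline score, as if still alive at that level.

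The visit tests therefore compare groups formed after randomisation. If one arm loses more patients, and they are the ones who were recovering poorly, those who remain look better for a reason unrelated to any effect on function. Tables 15.2.6.2.x and 15.2.7.2.x would show a p-value and confidence interval without saying that deaths had been left out.

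Deaths are to be expected here: follow-up runs 18 months, one entry route requires NIHSS of at least 11, and the protocol's planned failure rates include death. The first scheduled post-baseline BI is at V3 (Day 38). Without an early-discontinuation or unscheduled score, an earlier death enters no BI comparison at all, not even Endpoint.

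**Working it through.** **Inputs from the documents.** The plan states no expected difference, power or mortality for BI or NIHSS. I borrow the planned 100 per arm, which does reproduce. The adjusted failure rates are 0.95 × 0.26 + 0.05 = 0.297 and 0.95 × 0.08 + 0.05 = 0.126, and the continuity-corrected two-proportion formula at 80% power gives 100 per arm. The 26% and 8% include death, so they cap the planned 6-month mortality. SAP 2.6 says recruitment stopped early, so the true size is smaller.

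**Assumed.** Death rates, BI distributions and how strongly deaths follow function.

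**Step 1: mechanism by hand.** Each arm has 10 patients who, if alive, would score each of 5, 15, …, 95. All share one baseline, so change is score minus a constant. The lowest scorers die: 10 on placebo, 20 on ESL.

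- Patients with data: placebo mean (15 + … + 95)/9 = 55; ESL mean (25 + … + 95)/8 = 60. The Hodges-Lehmann shift is +5 for ESL, p = 0.21.
- Deaths ranked worst: the 20 ESL deaths tie with the 10 placebo deaths (0.5 × 20 × 10 = 100). ESL survivors score 250 + 350 + … + 950 = 4,800. P(ESL better) = 4,900/10,000 = 0.49, p = 0.81.
- With 30 ESL deaths: the shift is +10 (p = 0.015) among patients with data; P(ESL better) is 0.47 (p = 0.46) with deaths ranked worst.

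The apparent benefit comes wholly from who is left in the comparison.

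**Step 2: the coded variable.** Simulation with baseline BI 35 (SD 25), mean recovery 25, 100 per arm, no drug effect, 1,500 runs. Shift is ESL minus placebo in change from baseline, among patients with data.

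| Deaths, ESL / placebo | Deaths follow | Shift | Rejection (nominal 5%) |
|---|---|---|---|
| 20% / 10% | baseline BI | -0.3 | 5% |
| 20% / 10% | later function | +1.4 | 9% |
| 20% / 10% | recovery | +2.0 | 14% |
| 5% / 20% | baseline BI | +0.3 | 5% |
| 5% / 20% | later function or recovery | about -2 to -3 | up to 27% |

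A repeat for 20% / 10% with deaths following later function or recovery gave +1.3 to +2.0 and 8-16% rejection. On the BI score itself, deaths following baseline would shift the result by +2.2 (20% / 10%) or -3.5 (5% / 20%). Testing change from baseline removes that part.

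**Step 3: visit test, Endpoint and worst rank together.** A second model, 1,000 runs, 100 per arm, still no drug effect. Baseline is 35 (SD 25), V3 score = 0.6 × baseline + 22 + 18L, later score = 0.4 × baseline + 38 + 22L, with L standard normal. Scores are rounded to 5 and kept within 0-100. Deaths are selected on poor L with weight 0, 1 or 2. ESL deaths 20%, placebo 10%. Mean Hodges-Lehmann shift in change from baseline:

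| Selection weight | Patients with data | V3 value carried forward | Deaths ranked worst | Planned visit test significant for ESL (nominal 2.5%) |
|---|---|---|---|---|
| 0 | -0.1 | -1.0 | -5.2 | 2.7% |
| 1 | +2.2 | -0.5 | -3.1 | 9.8% |
| 2 | +3.1 | -0.4 | -2.1 | 13.9% |

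With 10% deaths in both arms every shift is within about 0.1 of zero. With 50 per arm and weights 1 and 2, the shift among patients with data is +1.9 to +2.7.

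The two models differ somewhat in size and agree in direction. Carrying the last value forward pulls an excess of deaths towards no difference; it does not turn it into a benefit.

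**The case against.** - **The tests carry little weight.** They are labelled exploratory, unpowered and unadjusted for multiplicity, and the protocol's synopsis planned only descriptive statistics for BI and NIHSS. This stands, and it limits how much the point matters.
- **Deaths are visible elsewhere.** Failure tables split out deaths by arm, overall survival has a log-rank test, fatal TEAEs have a table, and missing counts go with each summary. True, but showing deaths in another table does not correct the BI and NIHSS estimates.
- **Describing function while alive, beside survival, is a legitimate choice.** Agreed. Counting death as a failure in the primary endpoint does not oblige the sponsor to rank it worst on a functional scale. The choice should then be stated and labelled, which it is not.
- **The mortality scenarios are invented.** Also true. A 20% ESL mortality exceeds the planned 8% total ESL failure rate at 6 months. The 5% versus 20% pair fits under 8% and 26%, and there the bias runs against ESL. No document suggests that mortality will differ by arm.
- **Tempting stronger readings.** A reader might infer that severe entry strokes alone create the bias; on change from baseline, deaths that follow only baseline BI leave it near zero. A reader might also infer that the Endpoint rule makes the arm with more deaths look better. In the simulation the sign was slightly against that arm; it could favour it only if the last scores before death were relatively good. Nor do the documents support saying that the functional result will be reversed.

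**Conclusion.** The gap is real and modest. Following the SAP as written, deaths drop out of the V3, V5 and V7 tests and enter Endpoint at a value recorded alive, and no planned analysis of BI or NIHSS includes death.

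The visit tests are biased towards the arm with more deaths only if two conditions hold together: mortality differs between arms, and deaths fall on patients with poor later function or recovery. Under the assumptions of Step 2 this means about +1 to +2 BI points for 20% ESL versus 10% placebo deaths, and about -2 to -3 for 5% versus 20%, with 8-27% rejection instead of 5%. The second model reaches +3.1 at its strongest selection. Equal mortality, or deaths that depend only on baseline BI, gives about zero. Endpoint mainly hides the deaths.

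The sizes are illustrations, because the documents give no mortality rate. NIHSS was not simulated; the point there rests on its having the same structure.

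**What to change.** Before unblinding, in the FAS versions of Tables 15.2.6.2.x and 15.2.7.2.x:

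1. Add a supplementary Wilcoxon-Mann-Whitney test on the planned variable, change from baseline, at V3, V5, V7 and Endpoint. Rank patients who died by that time worse than every observed value. Any code below -100 for BI change and above +42 for NIHSS change does this, given score ranges of 0-100 and 0-42. Count a death by the slot's target day, even if a score before death was slotted there, and state which window Endpoint refers to.
2. Report its p-value, the probability that an ESL patient fares better, and deaths per arm. A Hodges-Lehmann shift on the coded values is not needed, since the code is arbitrary.
3. Leave the planned estimates unchanged. Label the visit rows *patients with data at the visit* and the Endpoint row *last value before death carried forward*. *Survivors only* would be wrong, because withdrawals drop out too.

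Cost: SAP wording and one row per time point. The survival analysis already needs the date of death, and the method is already rank-based. With one Endpoint window this adds 4 time points × 2 scales = 8 unadjusted exploratory p-values. The added result mixes survival with function, which is why the planned estimate stays beside it, and it does not address withdrawals.
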